31.1. Atrial, ventricular

32. Hours a day in AF, daily

Frailty (physical assessment, self-report questionnaire)

33. Physical frailty assessment – Fried criteria (24)

Self-reported PA

34. RAPA score (aerobic, strength and flexibility) (53)

Quality of life

35. Medical Outcomes Study Questionnaire Short Form 36 Health Survey (45)

Table 3: Long term conditions

Long Term Condition	Definition for study
Hypertension	
• Self-report• Coded on electronic medical records
Hyperlipidaemia	
• Self-report

	
 • Coded on electronic medical records • non HDL-cholesterol concentration >7.5mmol/L
Ischemic heart disease	
 • Self-report • Coded on electronic medical records • Previous myocardial infarction, coronary stent, or coronary artery bypass graft
Diabetes (type 1, type 2)	
 • Self-report • Coded on electronic medical records • HbA1c >48mmol/mol
Arthritis (osteoarthritis, inflammatory arthritis)	
 • Self-report • Coded on electronic medical records
Heart failure (left ventricular failure, heart failure with preserved ejection fraction)	
 • Self-report • Coded on electronic medical records • Echo demonstrating ejection fraction <40%
Depression	
 • Self-report • Coded on electronic medical records
Chronic kidney disease	
 • Self-report • Coded on electronic medical records • eGFR (estimated glomerular filtration rate) <60%
Osteoporosis	
 • Self-report • Coded on electronic medical records • T score < -2.5 on DEXA scan
Dementia (plus subtype if available)	
 • Self-report • Coded on electronic medical records
Chronic obstructive pulmonary disease	
 • Self-report • Coded on electronic medical records
Atrial fibrillation (permanent, paroxysmal)	
 • Self-report • Coded on electronic medical records • Device download data
Cancer (excluding skin squamous/basal cell carcinomas)	
 • Self-report • Coded on electronic medical records
Asthma	
 • Self-report • Coded on electronic medical records
Stroke/TIA	
 • Self-report • Coded on electronic medical records

	
• Brain imaging demonstrating previous ischaemic or haemorrhagic event
--	--

Withdrawal from Study

All participant derived data will be collected on the day of consent, bar the occasional case where a participant wishes to take the questionnaire home and post in back at a later date. Given the short period of time each participant will be actively enrolled in the study, it is highly unlikely a withdrawal of consent will occur. In the event of withdrawal of consent, a consent withdrawal form will be used to document this event. All data collected up to the date of consent withdrawal will be retained, but no further outstanding data collected. This will be made clear in the study information and consent form.

Statistical Analysis

Basic variables from CIED data

CIED data will be processed to create a new set of basic variables for analysis.

1. Mean daily physical activity (MDPA) – mean PA across dataset
2. PA intra-individual variability – as measured by:
 - Range
 - Interquartile range
 - Mean absolute deviation
3. PA surrounding NEHAs – multiple measures.

DOEDA = date of emergency department attendance; DOA = date of hospital admission; DOD = date of discharge; LOS = length of stay (DOD-DOA)

- Difference in PA from MDPA on DOEDA/DOA day -1, day -2, day-3, day-7, day -14
- Difference in PA from MDPA on DOEDA/DOD day +1, day +2, day+3, day+7, day +14
- ‘Time till PA recovery’ – time from DOEDA/DOD to day regained \geq MDPA

Descriptive analyses

All data will be stored and analysed using SPSS and ‘R’ statistical computing software. Basic descriptive statistics will be used to compare different sub-groups of participant (e.g. frail v non-frail). MDPA will be used to facilitate basic comparative analysis using a continuous variable. Determinants of MDPA will be calculated using univariate and multivariable analysis.

PA patterns

As demonstrated in *Figure 3* below, common activity patterns embedded within CIED PA data will be identified using clustering algorithms. Using these identified subtypes of PA as exposures in a longitudinal model with outcome NEHA, multilevel/hierarchical modelling methods (both classical and Bayesian approaches) will be utilised to investigate associations with outcome.

[figure not shown]

Figure 3

PA and major health events

For this study, major health events are defined as NEHA episodes. Daily PA in the days leading up to NEHA episodes will be compared to a participant's MDPA, in order to define across the cohort when any observable change in PA is detected by this method. To explore trends in PA preceding NEHA episodes, a nested case control study will be constructed within the dataset, comparing trends in PA preceding NEHA episodes with general trends in PA before index times with no NEHA episodes. This will allow the creation of various 'PA markers' for diagnostic test evaluation methods (sensitivity/specificity, positive and negative predictive value). These PA markers will then be investigated to ascertain if they predict PA subtypes i.e. long-term behaviour patterns. We will also look at how these 'markers' superimposed on identified subtypes can be used to potentially personalise alert systems.

In a similar fashion, we will also explore PA trends following NEHA episodes. There is very little published data on 'recovery time' following hospitalisation episodes in an older population. This study is not powered to investigate this as a primary outcome, however we will measure 'time till PA recovery' following NEHA subtypes (A&E attendance and non-elective hospitalisation episodes), and examine determinants of this.

Risks to Study

Recruitment

A snapshot 'screening' audit using Cardex data in October 2016 found 341 potentially eligible patients on CIED annual follow-up at Manchester Royal Infirmary, an additional 150-250 patients at Wythenshawe are anticipated to be eligible. Recruitment will be undertaken by the PI. An 18-month period has been allocated for initial recruitment. Based on observational studies in similar population, we anticipate a take-up rate of from screening of between 60-80% (56).

Efforts made to maximise recruitment:

- Rigorous screening process
- Recruitment from existing clinical visits
- Low burden of assessment

In the event of lower than anticipated take-up, the recruitment window could be extended beyond 18 months to reach required sample size.

Missing data

This is always a risk during any clinical study. Missing clinical data from electronic health records is expected. Missing data from device downloads is anticipated to be minimal. Self-report questionnaires have been designed to be as short as possible, with clear questions and minimal need for free-text. Questionnaires have been reviewed by the Manchester Academic Health Science Centre Public Patient Involvement panel (MAHSC PPI) to identify any misleading or unclear questions.

Data Management Plan

Description of the data

Directly acquired participant data will be quantitative, generated from; consent forms, questionnaires, physical frailty assessments, CIED downloads and electronic health records. Data from linked electronic health records will be ascertained through NHS Digital Hospital Episode Statistics. Collection and storage of personal, identifiable data will be kept to a minimum, using SPNs wherever possible.

Data collection / generation

All CtC forms returned to the research team by post will be stored in the site file(s). The screening and enrolment log will also be stored in paper format in the site file(s). Three paper copies of the signed consent forms will be produced – one for the participant to keep, one to be placed in the patient's hospital care file, and one to be retained by the study team in the site file(s). A paper case report form (CRF) will be created for each participant. This will be used by the researcher to record data collected during the physical frailty assessment and hospital electronic records. All participant questionnaires are in paper format.

Raw CIED data will be collected via a wireless receiver. See 'data collection processes above for further detail. The process of obtaining data from cardiac devices has been rigorously tested previously, and used as standard in clinical and research practice. This raw data will then be de-identified into SPN-coded format by the PI, before being transferred via secure end-to-end encrypted email to the technical team at the Medtronic Bakken Research Centre, Maastricht for processing. This SPN-coded data file is returned in the same fashion to the PI in an .xml file.

Linked HES data will be collected from NHS Digital via the Data Access Request Service (DARS) service. The NHS numbers of all participants (ascertained from health records) will be shared with the DARS service (via secure online portal), and linked HES data (with corresponding NHS number) will be returned to the PI via the portal. NHS Digital uses NHS standardised coded systems.

Data management, documentation and curation

See *Figure 3* below for an overview of the flow of data through the study.

[figure not shown]

Figure 3

Identifiable data will be collected on:

1. Consent to contact (CtC) forms
2. Consent forms
3. Screening log
4. Enrolment log
5. Linked HES data file

All other documents will be tagged with the SPN only.

One copy of the consent forms, the screening log, and the enrolment log are kept in the site file. The enrolment log will be used as a reference for linking identifiable data with SPNs. The completed SPQs and CRFs will be stored in the study participant files. Data from the SPQs and CRFs will be manually transcribed onto the electronic 'study data' database. Identifiable electronic data (linked HES data) will be stored in three secure locations: MHC research shared drive, an MFT designated research PC, and a designated research PC within the UoM.

All study data in paper format will be stored at the MFT. We have restricted the physical movement of data from the hospital site to the UoM as this is not required for data access by relevant staff – therefore would add an unnecessary complication. As per standard MHC research policy, the site file will be stored in stand-alone locked cabinets held in a secure location at the MFT. Study participant files will be stored in the locked MHC research office.

A single combined ‘research data’ database will be used for analysis (SPN-coded data only). In addition to allocated UoM PCs, this database will also be stored on a designated laptop will be encrypted by the UoM IT team. Metadata will be produced regarding data collection, management and analysis, in order for any secondary users to understand the data.

The study has been registered with the UoM Research Data Management Service (RDMS), where all electronic research data and associated metadata will be stored. This is an internal platform facilitating the storage, management, preservation, publication and sharing of research data.

Data security and confidentiality

UoM and MFT policies assure information security in line with recognised standards, and support compliance with relevant legislation. Personal data relating to the study will be stored securely in either paper or electronic format as laid out in *Figure 3*. All paper copies of study materials will be stored in either the site file(s) or study participant files. The site file(s) contain identifiable data, and will be kept on-site at the MFT in designated secure, stand-alone cabinets held in a secure location in the MHC. Study participant files contain all paper format SPN-coded data and will be stored in the MHC research office. The MHC research office is located in a ‘staff-only’ section of the hospital and is locked/occupied by research staff at all times. All identifiable study data in electronic format will be encrypted and backed-up, stored on secure designated locations only. Access to identifiable data will be granted to the PI, any additional research staff delegated to the PATTErn study, supervisory team and members of the clinical care team (in any case of clinical need). Authorised representatives from the UoM, NHS or regulatory bodies may be granted access to personal data for audit and monitoring purposes. All staff accessing study data will sign the delegation log in the HRA statement of activities file stored at the MHC research office. As per MFT/UoM policy, all members of staff with access to study material are fully trained in research ethics and IT security, bound to professional standards and accredited with up to date NIHR Good Clinical Practice (GCP) training.

The USB stick used to transfer CIED download .pdd files from the processor onto the trust PCs will be encrypted by MFT IT services. Once data has been safely transferred onto the PC, the USB stick will be wiped clean. The USB stick will remain on site in the MHC at all times.

A pseudo-anonymised, SPN-coded 'research data' database will be created for all analysis and only this data will be used and shared out with the study team as per the terms laid out in ethical guidelines, and consent forms. Due to the nature of the data collected, it is not feasible to create a fully anonymised database. Whilst re-identification will not be possible directly from the database, indirectly this may be possible if a person also has access to other confidential healthcare databases (for example, electronic patient records). This data will be stored on designated MFT and UoM computers.

PCs within the MFT and UoM have been identified for storing and processing the research data. Once the PC has loaded the operating system a local, password protected computer account is required to login to the PC. This account is unique to the primary user of the computer and only the account owner knows the password. Identified PCs have Windows firewall enabled and configured to prevent remote access. The PCs have been configured to automatically update their antivirus signatures daily and have been configured to download and install any Microsoft operating system and application security patches automatically from the Microsoft update service. The secure MFT and UoM servers will be used to store and back-up all electronic data daily.

In addition, a UoM encrypted laptop will be allocated to store SPN-coded research data and associated metadata only for the duration of the study. This will allow the PI to work with the data as part of her MD out with the trust/university sites. The PI will take full responsibility for the security of the laptop and follow UoM IT security protocols at all times.

Data archiving, sharing and access

All electronic research data and associated metadata will be stored with the UoM RDMS. Research data will be made available for other researchers and the public after results have been validated, presented, and published in peer-reviewed journals. Where we engage with commercial or other collaborators, and where appropriate, we reserve the right to share the data and analysis under Non-Disclosure Agreement.

Published data will be available through the UoM Current Research Information System. As per UoM policy, all peer-reviewed journal articles and conference papers will be open access, and accessible

via the Open Access Gateway. All Published outputs will be assigned a Digital Object Identifier to reference the data in publications.

Electronic study data will be retained until all study data is collected, processed and stored securely as research data (no longer than 24 months from start of study, see *Figure 1*). All paper documents will be retained in line with MFT policy. The consent form which is filed in the patient notes will be stored there indefinitely. All research data will be retained on the UoM RDMS, in possession of the UoM for a minimum of 20 years.

Responsibilities

The PI will take day-to-day responsibility for the quality of the data acquired, the datasets, and transfer for storage with the RDMS. Overall responsibility for the data will lie with the PI's primary academic supervisor at the UoM.

Dissemination of Results and Publication Policy

Results of this study will be disseminated to the academic community by publication in peer reviewed scientific journals, conference presentation and presentations at local academic meetings. Results will be disseminated to participants by letter, which will provide a summary of findings, and links to further information. We will also hold an event for participants and the public to explain the results of the study, for example through MICRA (Manchester Institute for Collaborative Research on Ageing) public event meetings. The wider public will be informed of findings through UoM media channels.

Project Management

This study will be co-ordinated by the PI. Study sponsor is the University of Manchester. Study development and delivery is supported by the Research and Innovation Division at Manchester University NHS Foundation Trust ([name] PhD Senior Divisional Research Manager).

Ethics

Ethical approval is mandatory for this study to commence. This shall be sought on confirmation of funding via the Integrated Research Application System (IRAS). This is a minimal risk observational study. Data collection at recruitment and follow-up has been scheduled to cause minimal inconvenience to patients and will coincide with appointments that constitute standard clinical care. The PI and all members of the research team are trained in assessing capacity to consent in clinical research.

Funding and Resources

PI ([name]) salary and data access costs will be funded by Medtronic. Study administrative costs will be met by research funds at the MFT. The project has been designed to be cost neutral to the host NHS trust.

References

1. National Service Framework for Older People, Department of Health for England, 2001.

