Every day, a huge volume of physiological data, including daily PA, is routinely collected by most modern cardiac implantable electronic devices (CIEDs). These devices are fitted in patients with cardiac conduction disorders and/or heart failure (HF). The average age of a patient undergoing implantation of a CIED in the UK is approximately 70 year old (14, 15). Older people with CIEDs are a cohort of patients with a particularly high risk of clinical frailty, hospitalisation and mortality (16-19). This therefore makes an ideal population to study PA patterns and temporal relationships with major health events.

CIED remote monitoring

Modern CIEDs continuously collect data for a host of physiological parameters relevant to cardiac function, including; heart rate, rhythm and variability, thoracic impedance, pacing time and PA. This data is stored within the device until it is ‘downloaded’ for analysis (for up to 14 months). For example, the Medtronic CareLink® Network allows patients to manually download data via a home monitor system as well as automatic programmed downloads ordered by clinicians (usually every 3 months from home, and an annual hospital based CIED check). Reports are then forwarded on to care providers for action. PA is considered ‘low’ if patients are ‘active’ (defined as >70 steps/min) for less than 60 minutes over a 1-week period (non-overlapping).

Existing evidence

Algorithms using CIED data to predict impending healthcare utilisation (HCU) have been in existence for a number of years, but are not yet integrated into standard UK clinical practice. The PARTNERS-HF study (20) tested a prediction algorithm based on a combination of 8 parameters (AF duration, ventricular rate during AF, fluid index, patient activity, night heart rate, heart rate variability, % of pacing CRT and ICD shocks) in HF patients with CRT defibrillators. Patients with parameters outside the norm for 2 or more domains triggered an alert for clinical action. Cowie *et al.* 2013 expanded the PARTNERS-HF dataset, totalling 921 HF patients, mean age 67-68 years (21). 30-day HF hospitalisation rates in the high-risk group were 10 times higher than in the low risk groups, HR (hazard ratio): 10.0; 95% CI: 6.4–15.7, P, 0.001. ‘Low’ versus ‘high’ PA was the most common domain trigger, contributing to over 80% of high-risk alerts. Low PA as a single domain was associated with a 2-3 fold increased risk of HF hospitalisation (HR 2.5, P<0.001).

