CIEDs include pacemakers, implantable cardiac defibrillators (ICDs), and cardiac resynchronisation devices (CRT). NICE guidelines (National Institute for Health and Care Excellence) recommend CRT device implantation as a *treatment option* for HF patients with prolonged QRS interval on electrocardiogram and an ejection fraction of 35% or less (37). CRTs have been shown to improve symptoms and slow progression of HF in randomised control trials (RCT) (38, 39). The MIRACLE study (38) (an RCT of 453 patients with moderate to severe HF randomised to CRT versus medical therapy) demonstrated CRT patients experienced a median change in 'distance walked in 6 minutes' of +39m at 6-month follow up (median: +39m, 95% CI +26 to +54, compared to control median: +10m 95% CI 0 to +25, where CI = confidence interval). Evidence suggests the additional endurance effect of CRTs is diminished by 12 weeks of implantation (40), thus data from this time period will be excluded from analysis as PA data may not represent normal behaviour. This will also allow time for the

patient to recover from the procedure, and allow the device time to synchronise its settings. It is unclear how pacemaker or ICD implantation would affect PA, however one could expect some positive impact through better control of symptoms, or perhaps a psychological 'safety-net' for a more active lifestyle. Although some devices with tight pacing settings may limit exertion. We expect this impact to be very small.

Validity of frailty assessments

The Fried phenotypic based frailty assessments are well validated in the general population. We estimate over half of the patients recruited into the PATTERn study will have some degree of HF. One domain of frailty that may be less reliable in a HF cohort is weight loss – as this may fluctuate with fluid status. Significant weight loss within the criteria is defined as over 10% body weight in the preceding four years (or a measured BMI $< 18.5 \text{ kg/m}^2$). These criteria would not tend to capture patients whom have lost weight simply due to diuresis, therefore we do not anticipate this will alter validity of results. The Fried criteria have been used in a number of studies which include participants with HF (19, 41). The original validation study itself included patients with HF, who represented 4.5% of the original Cardiovascular Health Study cohort (42). Therefore, this assessment has validity in this context.

Generalisability of results

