A request will be made to DARS (data access request service, NHS Digital) for access to NHS Digital Hospital Episode Statistics (HES) data for each participant in the preceding 12 months. HES data will be requested twice during the study – at 6 months, and 18 months (a fee is associated with each request). HES data includes:

- Emergency department (ED) attendances
 - Date
 - Discharge destination
 - Main diagnostic codes from attendance
- Non-elective hospitalisation episodes
 - Date of admission
 - Date of discharge
 - Discharge destination
 - Main diagnostic codes from admission

- Discharge destination

Rationale for data collection process

Involvement of third party (Medtronic technical team)

Conversion of the CIED download file from .pdd to .xml format can only be done by Medtronic staff using internal software. Only pseudo-anonymised files will be shared with Medtronic. Please see data management plan (DMP) for further detail.

Use of USB stick

Transfer of data from the CIED processor to a computer can only be done using a portable USB stick.

Please see DMP for further clarification on data security.

Use of Southampton protocol for hand grip strength

The Southampton protocol for measuring handgrip strength is well established and has been used widely in large epidemiological studies involving older people. It is recommended by the European Working Party on Sarcopenia in Older People (49).

Use of HES data

MFT is a tertiary centre for Cardiology, therefore the local hospital for many device patients may be elsewhere within Greater Manchester. In order to ensure no NEHAs are missed, it is necessary to collect this data from NHS Digital, which monitors all hospital attendances on a national level.

Summary of data to be collected

Personal data (*hospital* records, self-report questionnaire)

1. Age (hospital records, verbally confirmed with patient)
2. Sex (self-report questionnaire)
3. Ethnicity (self-report questionnaire)
4. Postcode (hospital records)
 - 4.1. Index of deprivation measure
5. Type of accommodation (self-report questionnaire)
6. Living circumstances (self-report questionnaire)
7. Mobility aids (self-report questionnaire)
8. Care provision (self-report questionnaire)

Events/changes in care needs in preceding 12 months

9. Falls (self-report questionnaire)
10. Use of rehabilitation facilities in preceding 12 months (self-report questionnaire)
11. Frequency of use of primary care services (self-report questionnaire)

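### MDPA, the reference for PA changes around a NEHA, averages in the NEHA's own low-activity days, so it understates the size of a pre-NEHA drop and sets the recovery threshold too low

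*Combined protocol and SAP*

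**What the plan says.** The Statistical Analysis section, under Basic variables from CIED data, defines "Mean daily physical activity (MDPA) – mean PA across dataset". The same list gives MDPA three uses:

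- before the event: "Difference in PA from MDPA on DOEDA/DOA day -1, day -2, day-3, day-7, day -14";
- after the event: "Difference in PA from MDPA on DOEDA/DOD day +1, day +2, day+3, day+7, day +14";
- recovery: "time from DOEDA/DOD to day regained" a level of at least MDPA.

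Under PA and major health events, the plan makes clear that MDPA is the participant's own mean. Daily PA before a NEHA is compared with it "in order to define across the cohort when any observable change in PA is detected by this method".

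The one stated removal of PA days is in Impact of CIED implantation on results. It covers the 12 weeks after implantation: "thus data from this time period will be excluded from analysis as PA data may not represent normal behaviour". Nothing comparable is stated for days around a NEHA.

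**The concern.** Under Expected outcomes, the protocol anticipates an acute fall in PA before NEHAs. If that is right, the days just before a NEHA, the days in hospital and the days of recovery are all below usual, and all of them enter the mean against which the fall is judged. The plan accepts that unrepresentative days should be left out after implantation, but does not apply this to NEHA days.

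Objective 4 is to confirm or refute the pre-NEHA drop, and the comparison with MDPA is the stated way to date its onset. A reference that is too low shrinks the measured drop. It can also hide an early, shallow decline, so that onset is dated too late. The same low reference is the recovery threshold, so recovery is declared too early. The distortion grows with length of stay and slowness of recovery. It therefore differs between participants, and between the attendances and admissions whose recovery the plan intends to study.

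**Working it through.** **The plan's own figures.** The documents give no figure for MDPA, the size of the drop or day-to-day variation in PA, so there is none to reproduce. The event rate bears on repeat NEHAs and does reproduce: 224/659 = 0.34 per patient-year, and 0.34 × 150 = 51 NEHAs (Sample Size Calculations).

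**Series length T, from the documents.**
- Devices hold data "for analysis (for up to 14 months" (CIED remote monitoring), about 425 days.
- The NEHA look-back is "Hospital Episode Statistics (HES) data for each participant in the preceding 12 months" (NEHA Episodes: DARS), 365 days.
- The shortest eligible series is 6 months in situ (Inclusion Criteria) less 12 weeks: 182 − 84 = 98 days.

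**Assumed shapes.** Usual PA = 1. PA is 0.8 on days −14 to −1 (true drop 0.200), 0.1 on inpatient days (or the one attendance day), and rises linearly from 0.5 to 1 during recovery (average loss 0.25 a day).

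**Formulas.** Loss = 14 × 0.2 + inpatient days × 0.9 + recovery days × 0.25. MDPA = 1 − loss/T. Measured drop = MDPA − 0.8 = 0.200 − loss/T.

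| Event (inpatient + recovery days) | Loss | Drop read, T = 365 | Drop read, T = 425 |
|---|---|---|---|
| ED attendance, 1 + 14 | 2.8 + 0.9 + 3.5 = 7.2 | 0.180 | 0.183 |
| Stay, 7 + 28 | 2.8 + 6.3 + 7.0 = 16.1 | 0.156 | 0.162 |
| Stay, 14 + 60 | 2.8 + 12.6 + 15.0 = 30.4 | 0.117 | 0.128 |
| Two 7 + 28 events | 32.2 | 0.112 | 0.124 |

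In the 98-day series, one 7 + 28 event gives 0.200 − 16.1/98 = 0.036.

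**With NEHA days left out.** Omitting days −14 to −1, inpatient days and 28 days after discharge, the first two events read 0.200. For 14 + 60, the 32 recovery days still in the reference carry a loss of about 4.27. The drop then reads 0.200 − 4.27/309 = 0.186 at 365 days and 0.200 − 4.27/369 = 0.188 at 425. Omitting 60 days restores 0.200.

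**Recovery time.** This was simulated with independent normal daily noise, SD 0.15 (assumed), taking recovery as the first day at or above the reference. A true 28-day recovery reads 19.0 days with a clean reference and 16.5-16.9 with MDPA. A true 60-day recovery reads 34.2 and 24.6-26.0. The first-day crossing rule alone removes about 9 and 26 days; MDPA removes a further 2 and 8-10.

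**Long-term trend.** Take a steady fall from 1.15 to 0.85 over 365 days with no acute drop. The day −1 difference from MDPA averages +0.11 for first-quarter events and −0.11 for last-quarter events. With a NEHA-free mean (7 + 28 window) it averages +0.12 and −0.13. Leaving out NEHA days does not remove trend and slightly enlarges its effect.

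**The case against.** **The effect is small in the ordinary case.** For one ED attendance in a 12-14 month record, about 0.02 of a 0.200 drop is lost, and every shape above is assumed. This stands. The 98-day case also needs a device only just six months in place, while recruitment is at annual device follow-up. The documents do not show how common short series are.

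**Repeat events.** A reader might infer that they are usual, because the heart failure study used as a guide had 224 visits in 132 patients (1.7 each). That ratio covers only patients with a visit, and the protocol does not give the number enrolled, so it cannot be carried over to a 12-14 month series. At the protocol's 34% annual rate, Poisson counts would give 0.34/(1 − e^−0.34) = 1.18 NEHAs per affected participant, with 16% of those having two or more. Clustering would raise this by an unknown amount.

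**Objective 4 does not rest on MDPA alone.** A reader might infer that the whole test of a pre-NEHA drop is compromised. The documents do not support that. The nested case-control comparison and the markers built from it do not name MDPA as their reference. Within a participant the error is also a constant offset, so the shape from day −14 to day −1 is preserved.

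**Trend can be the larger error.** In the example above it exceeds the bias from a single ED attendance or 7 + 28 stay, and a NEHA-free mean does not cure it. This stands and shapes the fix.

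**Recovery is secondary.** The plan says the study is not powered for it as a primary outcome, and most of the shortening has another cause. Both are correct.

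**Conclusion.** The concern holds for the quantities measured against MDPA: the pre- and post-NEHA differences, the dating of the first detectable change, and the recovery threshold. Other things equal, MDPA is too low by lost activity divided by series length. The direction follows by arithmetic whenever PA is below usual around a NEHA. The amount is conditional on the assumed shapes: in a 365-425 day series with one event, a true drop of 0.200 loses about 0.02 (ED attendance) to 0.08 (14-day stay, 60-day recovery). It loses more in short series and with repeat NEHAs, whose frequency the documents do not give.

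It would go too far to say that MDPA always understates the drop, since a long-term trend can move the difference either way, or that MDPA is the main reason recovery looks short. The sample size does not depend on MDPA. This should be fixed before analysis; it does not undermine the design.

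**What to change.** 1. Keep whole-series MDPA as a descriptive variable and as a sensitivity analysis.
2. For the pre- and post-NEHA differences and the recovery threshold, use the participant's mean over days outside a prespecified window around every NEHA: days −14 to −1, inpatient days and, for example, 28 days after discharge, with 60 days as a sensitivity analysis. State a minimum number of reference days and report how many NEHAs lack it.
3. Compute the same type of reference at the NEHA-free index times already planned, taken at a similar time before download, and report the case-minus-control difference. This step is what deals with trend. Index times have no length of stay, so the plan must state which days are left out for them.
4. For any marker evaluated for prediction, use only days before the tested window.

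**Cost.** Wording and programming, with no new data. There are fewer reference days: one 7 + 28 event removes 14 + 7 + 28 = 49, leaving 316 of 365 or 49 of 98. Two such events with separate windows leave 267 or none. With the 28-day window, some bias remains after slow recoveries (0.186-0.188 instead of 0.200 in the 14 + 60 case). Days without HES cover cannot be confirmed as NEHA-free. How many there are depends on whether the 12 months count back from the download or from the HES requests at study months 6 and 18, which the protocol does not state and should settle.
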